4.5. Immunogenicity and Safety Variables

The following section describes the collection of immunogenicity and safety variables. For a detailed schedule of activities, refer to [Table 2](#). For a list of the primary and secondary immunogenicity and safety variables, refer to [Section 3.2](#) and [Section 8](#).

4.5.1. Adverse Events

4.5.1.1. Reactogenicity Events

Solicited AEs are pre-specified local and general (systemic) adverse events that are common and known to occur or are of particular interest following administration of the study vaccine. For this trial, solicited AEs will be assessed by study staff 30 minutes after each vaccination and then by study subjects daily for 7 days (day of vaccination and subsequent 7 days). Subjects are provided a diary card for recording the presence or absence and severity of solicited AEs.

Investigators will review diary cards with the subject and document positive findings on source documents or progress notes.

Solicited reactogenicity events include the following:

Local Reactions:

- Site pain, site tenderness, swelling, induration, site redness and pruritus.

Systemic Reactions:

- Fever, nausea, vomiting, abdominal pain, diarrhea (loose stools), appetite change, fatigue, headache, myalgias, arthralgias and malaise.

4.5.1.2. Unsolicited Adverse Event

Refer to Section 3.3.1 in this report or Section 11.5 in the protocol for a more detailed definition of AE. The occurrence of an AE might come to the attention of study personnel during study visits or during interviews of a study subject who presents separately for medical care. Information to be collected on AEs includes event description, time of onset, assessment of severity, relationship to study product (assessed only by the PI), and time of resolution/stabilization of the event. Unsolicited Adverse Events are non-serious adverse events occurring from the time of each study injection through approximately 28 days after each injection.

4.5.1.3. Serious Adverse Event (SAE)

Refer to Section 3.3.2 in this report for the definition of SAE. SAEs are collected from the time of first study injection through last study visit or last contact.

4.5.2. Severity of Adverse Events

All AEs will be assessed for severity by the investigator. The investigating team will execute the investigator severity scale below. Inherent in this assessment is the medical and clinical consideration of all information surrounding the event including any medical intervention required. Each event will be assigned one of the following categories: mild, moderate, severe, or potentially life-threatening. See Table 4 for vital signs and Table 5 and Table 6 for laboratory values for further guidance in the assignment of severity. The following criteria may be used for any symptom not included in the grading scale. The eCRF for AEs will reflect only the highest severity for continuous days an event occurred.

• Mild (Grade 1)	Does not interfere with routine activities Minimal level of discomfort
• Moderate (Grade 2)	Interferes with routine activities Moderate level of discomfort
• Severe (Grade 3)	Unable to perform routine activities Significant level of discomfort
• Potentially life-threatening (Grade 4)	Hospitalization or ER visit for potentially life-threatening event

FDA guidelines for toxicity will be followed; however, if a subject is evaluated in an emergency room for a non-life-threatening illness or symptoms (i.e., visits emergency department on weekend for mild problems because the physician's office is closed), the information from that visit will be reviewed, and severity of the AE will be assessed according to the subject's clinical signs and symptoms.

4.5.3. Immunogenicity Variables

Immunological analyses will be performed from blood samples drawn at follow up clinic appointments per the schedule in Table 2 to assess the immunologic responses to IM administration of Invaplex_{AR}-DETOX: 1) serum samples for antibody (IgG and IgA) titers against Invaplex; and 2) (IgG and IgA) titers against Invaplex from ALS. Reciprocal endpoint titers less than the starting dilution (LLOQ) of the assay will be assigned a value of half the starting dilution for computational purposes. In all statistics and listings, values <LLOQ will be presented as "<LLOQ", with LLOQ replaced with the actual starting dilution.

5. SAMPLE SIZE CONSIDERATIONS

A total of 60 subjects are planned for this study. The sample size for this study was limited by the early stage (Phase 1) of the product concept/testing and was designed to evaluate preliminary safety data but not designed to show statistically significant differences between groups. Given the small number of subjects per group, the precision of the estimate for AEs is limited. For example, using binomial probability formulae for no observed adverse events within the 16 subjects receiving a particular dose of the active vaccine yields a 95% CI of 0-21%.

6. GENERAL STATISTICAL CONSIDERATIONS

6.1. General Principles

All analyses will be grouped by dose (2.5, 10, 25 µg, placebo). In general, all data will be listed, sorted by dose and subject, and when appropriate by visit number within subject. All summary tables will be structured with a column for each treatment group in order of increasing dose, with placebos pooled at the end, and will be annotated with the total population size relevant to that table, including any missing observations.

6.2. Timing of Analyses

Blinded safety data through seven days after the third dose in each cohort will be prepared and reviewed by the Protocol Safety Review Team (PSRT) prior to enrollment into the next cohort. For details, refer to Section [6.6](#).

Once the full set of samples for key immunogenicity variables have been collected at the day 71 visit (28 days after the third vaccination), the database will be frozen for an unblinded (at the group level) topline results analysis.

A final analysis of all data collected through day 223 (by telephone) will be performed after all data queries have been resolved and the data base locked.

6.3. Analysis Populations

A summary of the analysis populations by study group will be prepared ([Table 8, Appendix A](#)).

6.3.1. Safety Population

The safety population will consist of all subjects who received at least one immunization. Subjects will be grouped according to the actual product received. This population will be used for all safety analyses. Denominators for different safety endpoints may vary according to the number of subjects with available data for the specific endpoint.

6.3.2. Immunogenicity (IMM) Population

The immunogenicity population will be adapted to each analysis time point and parameter, and will include all subjects who received at least two vaccinations, who have baseline and post-vaccination data for the immunogenicity variable of interest. Subjects with missing baseline data, major protocol deviations prior to the analysis time point, that are likely to affect immunology results, or who only received a single vaccine dose, will be excluded.

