8.10. Stopping Criteria

The study will use a dose-escalation design to evaluate increasing doses of Invaplex_{AR}-DETOX.

The PI, along with the PSRT, may determine a subject's local site reactions warrant discontinuation of subsequent vaccinations for that subject. If it is determined that a subject will not continue with future vaccine doses, they may remain enrolled in the study for follow-up.

If any of the following events occurs, administration of investigational product will be discontinued for the group until a thorough review of the event is undertaken by the investigators and the PSRT:

- The occurrence of one serious adverse event determined to be related to the investigational vaccine (definitely, probably, or possibly) at any time post-vaccination.
- Severe diarrhea, defined as six or more liquid stools within 24 hours of vaccination.
- A severe local rash, defined as one that makes the subject unable to perform normal daily activities and which is not attributable to another cause.
- Systemic rash, including but not limited to generalized urticarial, generalized petechiae, or erythema multiforme, occurring in two or more subjects in a group will result in stopping further vaccination in subject's group.
- One vaccine-related serious or unexpected AE evaluated by the principal investigator (PI), Independent Research Monitor, and sponsor and determined to be an unacceptable risk to the health and safety of other investigational product recipients.
- If a subject experiences grade 2 or greater hypotension in the 30 minutes following vaccination, they will not be eligible to receive subsequent vaccinations.

Further vaccination, in accordance with the protocol, may be resumed with the concurrence of the PRST, sponsor's representative, the PI, and the US Food and Drug Administration (FDA).

An interim analysis for each cohort will be prepared and reviewed to include all safety data through seven days after the third vaccination dose for each cohort. This report will be provided to the PSRT for their review to determine whether the study can continue to enroll for the next, dose-escalating cohort or whether the study should be stopped. In addition to the interim safety analyses, the PI, sponsor's representative along with the PSRT will stop the study until further review by the PSRT if any of the following criteria that are thought to be definitely, probably, or possibly related to the investigational vaccine are identified:

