12.1.2. Analysis Addressing the Secondary Study Objective

For immunology responses, both qualitative (responder rates) and quantitative (e.g., \log_{10} transformed values) results will be analyzed. Geometric mean titers will be calculated for serological responses along with their 95% confidence intervals (or standard deviation). If appropriate, between groups comparisons will be examined with nonparametric median tests (Kruskal-Wallis for continuous data and Fisher’s exact test for categorical data) unless assumptions are fulfilled for Student’s t or χ^2 .

Additional comparisons may be made using repeated measures analysis of variance with study group as the between subject factor and sample collection time-points as the repeated factor. Only subjects who receive at least 2 vaccine doses will be included in the immunology analysis. All statistical tests will be interpreted in a two-tailed fashion using an $\alpha=0.05$ to represent statistical significance.

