12.5. Selection of Subjects to Be Included in Analyses

All subjects who receive at least one dose of the investigational product will be included in the safety analyses. All subjects who receive at least two doses of the investigational product will be included in the immunological analyses.

13. Direct Access to Source Data/Documents

Subjects will be identified on eCRFs by a unique subject identification number and on source documents by name and date of birth. No personal identifier will be used in any publication or communication used to support this research study. The subject identification number will be used if it becomes necessary to identify data specific to a single subject. Representatives of the sponsor, the local IRB, and the FDA are eligible to review medical and research records related to this study as a part of their responsibility to protect human subjects in clinical research. Personal identifiers will be removed from photocopied medical and research records.

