3.2. Study Endpoints

3.2.1. Primary Endpoints

3.2.1.1. Reactogenicity and Safety

Solicited local and general AEs through 7 days after each vaccination:

- Occurrence and severity of solicited local AEs including site pain, tenderness, swelling, induration, redness and pruritus in each study group.
- Occurrence and severity of solicited systemic AEs including fever, nausea, vomiting, abdominal pain, diarrhea (loose stools), appetite change, fatigue, headache, myalgias, arthralgias and malaise in each study group.

Unsolicited AEs post-vaccination:

- Occurrence and severity of unsolicited AEs from day 1 to day 71.
- Clinical laboratory abnormalities 7 days after each vaccination: Occurrence of hematological (red blood cells, white blood cells, differentials, hematocrit, platelet count and hemoglobin) or biochemical (sodium, potassium, glucose, AST, ALT, BUN and creatinine) laboratory-based adverse events in each study group.

Occurrence of serious adverse events (SAEs) at any time during the study.

3.2.2. Secondary Endpoints**IgG and IgA serologic and ALS responses to *S. flexneri* 2a Invaplex:**

The following aggregate variables will be calculated for the above parameters with 95% confidence interval (CI):

- Serum IgA and IgG geometric mean titers (GMTs) on days 1, 22, 43, 50, 57 and 71.
- ALS IgA and IgG GMTs at baseline and on days 8, 29, 50 and 71.
- Percentage of subjects with a \geq 4-fold increase in serum IgA and IgG from baseline (day 1) to day 22 (21 days post-vaccination 1), day 43 (21 days post-vaccination 2), 7, 14 and 28 days post-third vaccination, and from baseline to any post-vaccination time.
- Percentage of subjects with a \geq 4-fold increase in ALS IgA and IgG from baseline to day 7 post each vaccination, day 28 post-third vaccination and from baseline to any post-vaccination time.
- Geometric mean fold-rise (GMFR) in serum IgA and IgG from baseline (day 1) to day 22 (21 days post-vaccination 1), day 43 (21 days post-vaccination 2), days 7, 14 and 28 post-third vaccination, and from baseline to any post-vaccination time.
- Geometric mean fold-rise (GMFR) in ALS IgA and IgG from baseline to day 7 post each vaccination and day 28 post-third vaccination.

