14.1 Description of Study Subjects

Table 7: Ineligibility Summary of Screen Failures [In-Text]

Inclusion/Exclusion Category	Inclusion/Exclusion Criterion	n ^a
Inclusion and Exclusion	Subjects failing any eligibility criterion	x
Inclusion	Any inclusion criterion	x
	[inclusion criterion 1]	x
	[inclusion criterion 2]	x
	[inclusion criterion 3]	x
Exclusion	Any exclusion criterion	x
	[exclusion criterion 1]	x
	[exclusion criterion 2]	x
	[exclusion criterion 3]	x
Eligible but not enrolled		x

^a More than one criterion may be marked per subject.

[To include all inclusion/exclusion criteria]

Table 8: Analysis Populations by Treatment Group

Reason for Exclusion	InvaplexAR 2.5 µg (N=X)	InvaplexAR 10 µg (N=X)	InvaplexAR 25 µg (N=X)	Placebo (N=X)	All Subjects (N=X)
Safety Population	n (%)	n (%)	n (%)	n (%)	n (%)
Subjects Included					
Received First Vaccination					
Received Second Vaccination					
Received Third Vaccination					
Immunogenicity Populations[*]	n (%)	n (%)	n (%)	n (%)	n (%)
Assay	Completed Visit and Data Available				
Serum IgA	Day 22 (3 wks post-vac.1)				
	Day 43 (3 wks post-vac.2)				
	Day 50 (1 wk post-vac.3)				
	Day 57 (2 wks post-vac.3)				
	Day 71 (4 wks post-vac.3)				
Serum IgG	Day 22 (3 wks post-vac.1)				
	Day 43 (3 wks post-vac.2)				
	Day 50 (1 wk post-vac.3)				
	Day 57 (2 wks post-vac.3)				
	Day 71 (4 wks post-vac.3)				
ALS IgA	Day 8 (1 wk post-vac.1)				
	Day 29 (1 wk post-vac.2)				
	Day 50 (1 wk post-vac.3)				
	Day 71 (4 wks post-vac.3)				
ALS IgG	Day 8 (1 wk post-vac.1)				
	Day 29 (1 wk post-vac.2)				
	Day 50 (1 wk post-vac.3)				
	Day 71 (4 wks post-vac.3)				

* Subjects with baseline and post-vaccination data, who received all required vaccinations prior to visit.

Table 9: Subject Disposition by Treatment Group

Subject Disposition	InvaplexAR 2.5 µg	InvaplexAR 10 µg	InvaplexAR 25 µg	Placebo	Total
	n	n	n	n	n
Screened*	na	na	na	na	
Enrolled/Randomized					
Received First Dose					
Received Second Dose					
Received Third Dose					
Received all 3 Doses					
Completed Visit 11 (Day 71)					
Completed Visit 12 (Day 223)					
Serology IgA or IgG Results Available					
Visit 01 (Baseline)					
Visit 04 (Pre-Dose 2)					
Visit 07 (Pre-Dose 3)					
Visit 09 (Day 7 post-vac.3)					
Visit 10 (Day 14 post-vac.3)					
Visit 11 (Day 28 post-vac.3)					
ALS IgA or IgG Results Available					
Screening					
Visit 01 (Baseline)					
Visit 03 (Day 7 post-vac.1)					
Visit 06 (Day 7 post-vac.2)					
Visit 09 (Day 7 post-vac.3)					

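### The two-dose immunogenicity rule removes valid post-dose-1 results (ALS Day 8, serum Day 22) because a later dose was not given, and SAP Table 8 appears to apply a different rule

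*SAP*

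**What the plan says.** SAP 9 runs all immunogenicity analyses on the population defined in SAP 6.3.2. That population "will be adapted to each analysis time point and parameter, and will include all subjects who received at least two vaccinations" and have the relevant baseline and post-vaccination data. The exclusion sentence names missing baseline data and certain major deviations before the time point, and then ends "or who only received a single vaccine dose, will be excluded". The protocol agrees with this. Section 12.1.2 states: "Only subjects who receive at least 2 vaccine doses will be included in the immunology analysis". Section 12.5 states: "All subjects who receive at least two doses of the investigational product will be included in the immunological analyses".

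SAP 3.2.2 lists post-dose-1 results among the secondary endpoints: serum titers, fold-rises and responder rates at Day 22, and the same for ALS at Day 8. For the ALS responder rate the times run "from baseline to day 7 post each vaccination, day 28 post-third vaccination and from baseline to any post-vaccination time". Tables A1 and A2 label the Day 22 serum sample as taken before dose 2.

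Of Table 8, SAP 6.3 says: "A summary of the analysis populations by study group will be prepared". The footnote to its immunogenicity rows reads: "Subjects with baseline and post-vaccination data, who received all required vaccinations prior to visit".

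**The concern.** A Day 8 or Day 22 result is complete before dose 2 is given. Under SAP 6.3.2 it is nevertheless discarded if dose 2 does not follow. The post-dose-1 responder rates, GMTs and GMFRs then describe subjects selected on something that happened after the measurement.

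That later event need not be unrelated to the response. Protocol 8.10 lets the investigator and the PSRT decide that a subject's "local site reactions warrant discontinuation of subsequent vaccinations for that subject", and such a subject may stay enrolled. Protocol 8.4 ends dosing after emergency unblinding and keeps the subject in the study visits. If reactions to dose 1 go with stronger or weaker antibody responses, or become more frequent with dose level, the loss is informative and may differ between the groups being compared. Vaccinated subjects are not replaced (SAP 4.4.3).

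There is also a practical problem. Two programmers could each follow the SAP, one using 6.3.2 and one using the Table 8 footnote, and build different Day 8 and Day 22 datasets. The N in Table 8 could then differ from the N in the result tables. The same subjects feed the between-group p-values shown for Day 22 in Tables A1 and A2 and for Day 8 in Tables A3 and A4.

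**Working it through.** **1. The two rules side by side.** Table 8 has serum at 5 visits x 2 isotypes = 10 rows and ALS at 4 visits x 2 isotypes = 8 rows, so 18 in all. The doses due before each sample follow from the schedule (Days 1, 22, 43).

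| Rows | Number | SAP 6.3.2 | Table 8 footnote, natural reading |
|---|---|---|---|
| ALS Day 8, serum Day 22 | 4 | at least two | one |
| ALS Day 29, serum Day 43 | 4 | at least two | two |
| ALS Days 50, 71; serum Days 50, 57, 71 | 10 | at least two | three |

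Only in the first line does the 6.3.2 rule depend on a dose that comes after the sample. The statement in 6.3.2 that the population is adapted to each time point does not help. Within that paragraph only the deviation clause is limited to what happened before the time point, and the single-dose exclusion has no such limit.

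**2. The plan's own precision figure.** For 0 events in 16, the exact two-sided 95% upper limit is 1 - 0.025^(1/16) = 20.6%, which matches the stated 0-21% (protocol 12.2, SAP 5). The same exact method, with n = 16 per active group, is used below.

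**3. Responder rate.** No rate of missed second doses is given, so 1 to 3 of 16 is an assumption. So is a result of 7/16 when every dose-1 recipient counts: 43.8% (95% CI 19.8 to 70.1). With a single-dose subjects removed, the rate lies between (7 - a)/(16 - a) if all of them responded and 7/(16 - a) if none did.

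- One removed: 6/15 = 40.0% (16.3 to 67.7) or 7/15 = 46.7% (21.3 to 73.4).
- Two removed: from 5/14 = 35.7% (12.8 to 64.9) to 7/14 = 50.0% (23.0 to 77.0).
- Three removed: from 4/13 = 30.8% (9.1 to 61.4) to 7/13 = 53.8% (25.1 to 80.8).

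**4. Between-group test.** This is the exact Fisher test over three active groups of 16 and 12 pooled placebo subjects, with assumed responder counts.

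- 2, 4 and 7 of 16, and 0 of 12: p = 0.034. Removing one 25 µg subject gives 0.060 if that subject responded (6/15) and 0.021 if not (7/15).
- 3, 5 and 7 of 16, and 1 of 12: p = 0.175. The same removal gives 0.256 or 0.141.

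One subject moves the result across 0.05 only when p is already close to it.

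**5. GMFR.** If a subjects have a fold-rise k times that of the rest, the GMFR of all 16 is k^(a/16) times that of the rest. With an assumed k = 4, the factors are 4^(1/16) = 1.09, 4^(2/16) = 1.19 and 4^(3/16) = 1.30 for one, two and three such subjects.

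**6. How likely any loss is.** With an assumed chance d of missing dose 2, the probability that a group of 16 loses at least one subject is 1 - (1 - d)^16. This is 27.6% at d = 2%, 56.0% at 5% and 81.5% at 10%.

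**The case against.** The strongest reply is that the governing rule is consistent and deliberate. SAP 6.3.2 and two protocol sections all say two doses, and the notes to protocol Tables 3 and 4 show the same restriction in earlier Invaplex trials. Table 8 is only a summary shell. Its footnote prints no number and can be read as a further condition on top of 6.3.2. On that reading nothing conflicts, and aligning one footnote would be enough. A common two-dose set also keeps early and late visits on nearly the same subjects, which suits the optional repeated-measures analysis in protocol 12.1.2. Finally, exclusions would be visible in Tables 8 and 9, Listing 1 and the individual titers in Listings 6 to 9.

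Part of this stands. One dose at Day 8 and Day 22 is an inference from the footnote, not its text. Correcting the footnote alone would make the documents agree. It would not remove the selection on a later dose, which is in 6.3.2 itself. The earlier trials paired the two-dose restriction with having a post-dose-2 blood sample, so they give no reason to discard a post-dose-1 result. Listings allow a reader to rebuild the fuller set, but the reported rates and intervals would still rest on the selected one.

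Two stronger readings go too far. A reader might infer that the rules also clash at Days 50, 57 and 71, so that three doses should be required there. The footnote and 6.3.2 can be read together at those visits, protocol 12.5 includes two-dose subjects, and a three-dose rule would newly remove subjects whose dose was withheld because of a reaction. A reader might also take protocol 9.6.1 to require immunogenicity follow-up after dosing stops. It says only that those who continue are not counted as withdrawn, and 8.10 says they may remain. Only 8.4 makes continued visits definite.

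**Conclusion.** The concern holds for ALS Day 8 and serum Day 22. These listed secondary endpoints are conditioned on receipt of a dose that comes after the sample and that the reaction to dose 1 can prevent. The Table 8 footnote points to a different rule for these rows without stating it.

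The effect is small and conditional. It is zero if everyone receives dose 2, and SAP 6.5 expects minimal missing data. One single-dose subject among 16 shifts a rate near 44% by 3 to 4 points in an unknown direction, well inside the width of the interval. The responder counts, the number of single-dose subjects and the fourfold contrast are all assumed.

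A reader might see 7/16 become 7/14 = 50.0% and infer that the immunogenicity hypothesis could turn on this rule. The documents do not support that, because the hypothesis of at least 50% responders names no time point. Nor does the p-value example threaten a main conclusion. The tests are unadjusted and exploratory (SAP 6.7), and the study was not designed to show group differences (SAP 4.2). Safety analyses use a separate population, and escalation rests on safety alone. It is worth correcting because the repair is cheap and needs no new data.

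**What to change.** - In SAP 6.3.2, for ALS Day 8 and serum Day 22 only, include every subject who received dose 1 and has a baseline and that result, regardless of later doses. Leave the other exclusions unchanged.
- Report the at-least-two-dose set at these two visits as a sensitivity analysis.
- Keep the protocol's two-dose rule at all later visits and for the endpoint covering any post-vaccination time. That endpoint is not tied to one dose, and the rule avoids pooling subjects who have one early sample with fully sampled subjects. Some conditioning on dose 2 remains there, and the SAP should say so.
- Reword the Table 8 footnote to give the number of doses: at least one for ALS Day 8 and serum Day 22, at least two for every other row. It then no longer suggests three at Days 50, 57 and 71.
- Amend protocol 12.1.2 and 12.5 to match, and record the change in SAP section 12. Do this before the Day 71 group-level unblinding (SAP 6.2), so that the choice cannot be informed by results.

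The cost is one set of sensitivity tables and a protocol and SAP amendment (protocol 12.4), which needs sponsor agreement and approval before it takes effect (protocol 15.1.2). The subject set may also differ slightly between early and later visits, which should be noted wherever time courses are shown.
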